7.2. Viability and improvement in left ventricular ejection fraction

A Cox proportional hazards model will be used to assess the relationship between the number of viable myocardial segments (treated as a linear effect) and recovery of left ventricular function at six and twelve months. Multivariable Cox analyses will be used to adjust the analysis for the list of baseline factors in section 7.1. The interaction between viability and treatment assignment on improvement in left ventricular function will then be assessed using a Cox proportional hazards model containing the following co-variates: viability (treated as a linear effect), randomly assigned treatment, and their interaction, plus the aforementioned list of baseline risk factors. In secondary analyses, the extent of viability will be divided into tertiles and Kaplan-Meier curves stratified by both viability tertile and treatment assignment presented. A sensitivity analysis will be performed where viability is defined irrespective of resting dysfunction (including segments with normal function at rest and with $\leq 25\%$ scar on CMR or contractile reserve on DSE).

The relationship between the number of viable segments and recovery of left ventricular function will also be assessed using the change in ejection fraction at 6 and 12 months with a linear mixed effects model for repeated measures adjusting for the variables specified in section 7.1⁷. This model accounts for the baseline ejection fraction, while also incorporating both follow-up measurements, and enables the inclusion of participants with missing measurements. The mean change in ejection fraction at each timepoint along with the association between viability and these means will be estimated. The model includes a variable for time, viability, and an interaction between time and viability, and assumes no effect of treatment at baseline. An unstructured variance-covariance matrix will be used to allow for correlations between repeated measures of ejection fraction. The model will be fitted using restricted maximum likelihood and assumes that missing ejection fraction values are missing-at-random.

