9.2.1 LVEF on Echocardiography at 6 Months and 1 Year

Baseline, 6-month and 12-month echocardiograms will be anonymised and submitted to an independent echocardiography core laboratory (at Guy's and St Thomas' Hospital, London, UK), which will determine LVEF using a Simpson's biplane method for evaluation of the major secondary outcome. Anonymised scans were read by core laboratory readers who were blinded to treatment assignment and also the timing of each echo in relation to randomisation.

Where echocardiograms were not performed at precise follow-up intervals (for example, due to restrictions related to the COVID-19 pandemic), echocardiograms recorded between 4 months to 9 months post-randomisation will be considered as the planned 6-month measure, those recorded from 9 months to 24 months post-randomisation will be considered as the planned 1-year measure and the mean (SD) delay from randomisation to each echocardiogram reported. For patients who die a

value of 0% will be imputed for the primary analysis with a secondary sensitivity analysis excluding these patients.

The mean % LVEF at 6 months and 1 year in each treatment group, together with the absolute difference between these measures (and its associated p-value and 95% confidence interval), will be estimated using a linear mixed effects model for repeated measures as described by Frost, Kenward and Fox.¹

This linear mixed model is an extension of a simpler model suggested by White and Thompson as an alternative to the standard analysis of covariance (ANCOVA) model commonly used for the analysis of clinical trials with only a single follow-up measure of the outcome plus a baseline measure. Key features of the White and Thompson model are that the baseline measure is included in the model as an additional outcome that is allowed to be correlated with the follow-up measure, and whose mean is assumed to be the same in both arms of the trial. In the absence of missing data, the White and Thompson model gives identical effect estimates and virtually identical standard errors to the more standard ANCOVA model. Where there are missing data, the White and Thompson approach has the advantage that patients for whom the follow-up measure is present but the baseline measure is missing can be included in the analysis. It also extends naturally to the model proposed by Frost, Kenward and Fox for the situation where there are multiple follow-up measures.

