6.2. Secondary outcomes

While several secondary clinical outcomes were specified in the main trial protocol, for the Viability Study SAP, these will be restricted to all-cause death, cardiovascular death and heart failure hospitalisation, each analysed in the same manner as the primary composite outcome. Improvement of left ventricular function at six months is the key secondary outcome and will be defined in a binary manner, as an improvement in LV ejection fraction greater than the median change in LVEF at six months.

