6.4. Missing data

Missing viability data will not be imputed – participants whose viability studies are either not available or are not suitable for analysis will be excluded. For patients who have survived more than 6 months, missing values of ejection fraction will be imputed using multiple imputation by chained equations

with randomised treatment, age, sex, and baseline, 6-month and 12-month ejection fraction included in the imputation model. Twenty imputed datasets will be generated and effect estimates and corresponding confidence intervals calculated using Rubin's rules. Other rules for handling missing data will follow the main trial SAP. A sensitivity analysis will be performed limited to patients who have echocardiography data available at baseline and 6-months.

7. Statistical analysis

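### The viability SAP imputes 12-month LVEF for patients who die between 6 and 12 months, where the main SAP assigns 0%

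*Protocol*

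**What the plan says.** Main SAP, section 9.2.1, covers LVEF at 6 months and 1 year. After a death, a "value of 0% will be imputed for the primary analysis with a secondary sensitivity analysis excluding these patients". The same section counts echocardiograms from 9 to 24 months as the 1-year measure.

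Viability Study SAP, section 6.4, has its own rule: "For patients who have survived more than 6 months, missing values of ejection fraction will be imputed using multiple imputation by chained equations". Its imputation model contains treatment, age, sex and EF at all three times. On anything else the section says: "Other rules for handling missing data will follow the main trial SAP". A sensitivity analysis is limited to patients with baseline and 6-month echocardiography.

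Viability Study SAP, section 6.2, defines the key secondary outcome in binary form, "as an improvement in LV ejection fraction greater than the median change in LVEF at six months". No 12-month threshold is given.

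Viability Study SAP, section 7.2, nevertheless takes both times: its first Cox model concerns "the number of viable myocardial segments (treated as a linear effect) and recovery of left ventricular function at six and twelve months". It adds a mixed model for EF change at both times that "assumes that missing ejection fraction values are missing-at-random". It does not mention death.

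**The concern.** The survival condition in 6.4 suggests that its authors did not mean to give EF values to the dead. The condition stops at 6 months, but the analysis in 7.2 runs to 12. Patients who die in between satisfy it, so their absent 12-month EF is filled with a value appropriate to a living patient. The main SAP scores the same patients on the same measure at 0%.

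At stake is the 12-month half of an analysis that serves the viability study's primary objective, which includes LV functional recovery. Some of the patients with the worst course could be labelled recovered. Viability is not among the variables listed for the imputation model, so the imputed values carry no direct information on the exposure under study. The 6-month and 12-month results would also treat death differently.

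**Working it through.** **1. One patient through the rules.** Take a patient who dies at month 8 with no 1-year echo.

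| Rule | 12-month EF | Recovered at 12 months? |
|---|---|---|
| Main SAP 9.2.1, main analysis | 0% | No: change = 0 − baseline, always negative |
| Viability SAP 6.4, multiple imputation | Drawn given treatment, age, sex and the patient's own EF values | Possible |
| Viability SAP 7.2, mixed model | Missing at random | Not binary |

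The "no" in the first row assumes a threshold that is not itself strongly negative. The 6.4 sensitivity analysis does not expose the problem: if this patient had a baseline and a 6-month echo, the patient stays in it.

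**2. How many patients.** The documents give no deaths for this window, so the count is an assumption. It uses mortality quoted in the protocol's background (2.3 and 2.4) for other cohorts. The denominator is 491 CMR + 187 DSE = 678, a maximum because patients could have both tests and unusable studies are excluded. With constant hazard h = −ln(1 − p)/m per month, deaths in the window = 678 × (exp(−6h) − exp(−12h)).

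| Source | p at m months | Deaths, months 6–12 |
|---|---|---|
| Earlier PCI cohort, 6% at 6 months then constant hazard | 33% at 51 | 28.1 |
| Earlier PCI cohort, constant hazard | 33% at 51 | 29.8 |
| Surgical trial, CABG arm (2.3) | 36% at 56.4 | 30.0 |
| Surgical trial, medical arm (2.3) | 41% at 56.4 | 35.0 |
| Surgical trial, medical arm (2.4) | 46% at 56 | 40.5 |

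For the first row, h = ln(0.94/0.67)/45 and deaths = 678 × 0.94 × (1 − exp(−6h)). The range is about 28 to 41. Protocol 2.3 and 2.4 give different figures for the same medical arm; with the 2.3 figure the top is 35. All these counts are upper-end, since a patient who dies after month 9 may already have an echo that qualifies as the 1-year measure.

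**3. What share would be scored recovered.** No figure for this stands in the documents. Baseline, 6-month and 12-month EF were simulated as trivariate normal (400,000 draws). The 12-month value for patients who die was drawn from its regression on baseline and 6-month EF. Recovery was a 12-month change above the median 6-month change.

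- From the documents: SD 11 (protocol 8.1, main SAP 4.2).
- Assumed: correlation 0.5 or 0.7; cohort mean 28% at baseline and 30% at 6 months; 0 or 2 points of further gain by 12 months; EF deficits of 0, 4 or 8 points in those who die; the six-month threshold carried to 12 months.

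| EF deficit in patients who die | Corr. 0.5, no gain | Corr. 0.7, no gain | Corr. 0.5, +2 | Corr. 0.7, +2 |
|---|---|---|---|---|
| None | 49.8% | 50.0% | 57.1% | 59.2% |
| 6-month only, −4 | 45.1% | 42.4% | 52.3% | 51.6% |
| 6-month only, −8 | 40.5% | 35.0% | 47.7% | 43.9% |
| Baseline and 6-month, −4 | 54.6% | 53.4% | 62.1% | 62.6% |
| Baseline and 6-month, −8 | 59.3% | 56.7% | 66.4% | 65.6% |

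The range is 35% to 66%.

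**4. Combined.** 28 × 0.35 ≈ 10 and 41 × 0.66 ≈ 27. So roughly 10 to 27 patients per imputed dataset would be scored recovered, against none under the 0% rule.

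**The case against.** The best defence is that EF after death is undefined rather than missing. On that view the 6.4 imputation was meant for the living, and the sentence "Other rules for handling missing data will follow the main trial SAP" brings in the main SAP's 0% rule. This is a fair reading of intent, but the text does not say it. The sentence reaches only rules that 6.4 has not already given, and 6.4 has given one for everyone who survived more than 6 months. Two analysts could score these patients in opposite ways.

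Other parts of the defence stand:

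- The key secondary outcome is recovery at six months. Patients who die later were alive then, so imputing a missing 6-month value is legitimate. Section 7.3 uses that binary outcome in patients free of a primary event in the first six months, and is likewise untouched.
- A reader might infer that about half of these deaths count as recovered. That needs a 12-month threshold the plan does not state, patients who resemble survivors at baseline and 6 months, and no further gain in the cohort. The draw is conditional on each patient's own history.
- A reader might also turn the count into a bias. Section 7.2 estimates an association and an interaction with treatment, not a recovery rate. If the median were recalculated at 12 months, the overall rate would sit near 50% by construction. A shift in the rate is therefore not evidence of bias in what 7.2 estimates.
- Scoring death as non-recovery mixes mortality into a functional measure, and other choices are defensible. It is, however, consistent with the rule the main SAP already adopts.

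**Conclusion.** The point holds for the 12-month analyses in Viability SAP 7.2 only. As written, 6.4 assigns a living patient's 12-month EF to those who die between 6 and 12 months without a 1-year echo, and the 7.2 mixed model treats them as missing at random, in conflict with main SAP 9.2.1. Some of these patients would be scored recovered at 12 months.

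The size rests on mortality borrowed from other cohorts, a maximum denominator, assumed EF correlations and means, and a six-month threshold carried to 12 months. The documents do not support a claim that the six-month outcome is compromised, nor any stated size or direction of bias in the viability association or its interaction with treatment. The change is worth making because it removes a conflict between two plans for one trial.

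**What to change.** In Viability SAP 6.4, impute EF at each time point only for patients alive at that time point. In the 12-month binary analysis, score patients who died earlier as not recovered, consistent with main SAP 9.2.1, and add a survivors-only sensitivity analysis. In 6.2 or 7.2, state the 12-month recovery threshold: the six-month median carried over, or a 12-month median with the patients from whom it is computed. In 7.2, state how deaths enter the mixed model.

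The cost is a few sentences in the viability SAP and no new data.

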7.3. Improvement in left ventricular function and event-free survival

A Cox proportional hazards model will be used to assess the relationship between the improvement in left ventricular function (as a binary effect) on the primary outcome. Multivariable Cox analyses will be used to adjust the analysis for the list of baseline factors in section 7.1. The interaction between improvement in left ventricular function and treatment assignment on even-free survival will then be assessed using a Cox proportional hazards model containing the following co-variates: improvement in left ventricular ejection fraction (treated as a binary effect), randomly assigned treatment, and their interaction, plus the aforementioned list of baseline risk factors. Kaplan-Meier plots will be presented stratified by improvement in left ventricular function and treatment assignment presented. These analyses will be limited to patients who did not experience a primary outcome event in the first six months after randomisation. In secondary analyses, change in left ventricular ejection fraction will be treated as a linear effect.

8. Appendix 1: Cardiac Magnetic Resonance Secondary Analyses

This appendix describes subsequent planned analyses based on CMR data alone.

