2.2. Hibernating Myocardium

The concept of viable but dysfunctional myocardium emerged approximately three decades ago, when it was observed that patients undergoing coronary artery bypass surgery for chronic stable angina had improvement or normalisation of left ventricular function following revascularisation(5). The energy utilized during myocyte contraction far exceeds the requirement for sustaining viability and, as such, myocardial tissue may survive in a hypocontractile state in the presence of reduced coronary blood flow or decreased coronary flow reserve, known as hibernation(6). Improvement of blood flow by revascularisation of hibernating myocardium can lead to restoration of regional and global left ventricular function and reversal of adverse remodelling(7-9), provided this is achieved before the onset of irreversible cellular and ultrastructural alterations(10). Potentially reversible, dysfunctional myocardium is characterised by preserved cellular integrity and a degree of contractile reserve, whereas scarring and absence of inducible contraction tend to reflect irreversible myocardial damage. Each of these distinguishing features can be used to predict myocardial viability or the likelihood of functional recovery following revascularisation. The parameter most widely used to determine viability is contractile reserve, which is assessed by measuring the augmentation of function of hypocontractile myocardium, in response to inotropic stimulation. The most commonly used agent is Dobutamine (at doses up to 20 µg/kg/min) while the change in regional and global contractility could be imaged by dobutamine stress echocardiography (DSE) or cine-magnetic resonance imaging (MRI). While MRI allows scar imaging as well as assessment of contractile reserve, at present it is contraindicated in patients with implantable cardioverter defibrillators or pacemakers in situ, which can limit its use in a heart failure population.

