8.1. Power Calculation

The predicted occurrence of death or hospitalisation for heart failure at two years is 36% in the OMT group(8, 19, 31, 41, 42). The primary endpoint in REVIVED-BCIS2 will be measured over the entire trial duration, with a minimum follow-up duration of two years, thus increasing the number of events. A trial of 700 (350 in each group) with 300 patients experiencing an event would have over 85% power to detect a hazard ratio of 0.7 (a 30% relative reduction in the hazard) at 5% significance allowing for up to 5% losses by the end of follow-up and increasing recruitment over time. For illustrative purposes this represents a reduction in death or hospitalisation to 27% in the PCI group at two years. The hazard ratio of 0.7 used in the power calculation is pragmatic, while being clinically meaningful and is in line with the magnitude of benefit observed across other treatment modalities in this population.

For the major secondary endpoint, even half this sample size will provide 90% power to detect a minimum difference in EF of 4%, assuming a standard deviation of 11%. The trial is expected to have very good power to detect differences in Quality of Life (one of the major secondary outcomes).

The above predicted event rates take into account the possibility of patients randomised to OMT subsequently undergoing PCI (see below). If a higher event rate is found in the OMT group or patient recruitment rates exceed expectation early in the trial (thus providing a

longer duration of follow-up in a larger proportion of patients), the trial would have greater power to detect a hazard ratio of 0.7, or alternatively, provide over 85% power to detect smaller differences in treatment effect.

Although a smaller treatment effect may be clinically significant, this would have a major impact on sample size, which in turn may affect the feasibility of completing the trial within the proposed timescale and resources.

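### Viability Study SAP 7.3 compares PCI with OMT within strata of six-month LVEF improvement, which is measured after randomisation and expected to be moved by PCI, so these are not randomised comparisons

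*Protocol*

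**What the plan says.** Section 6.2 of the Viability Study SAP makes improvement in left ventricular function at six months the key secondary outcome, "defined in a binary manner, as an improvement in LV ejection fraction greater than the median change in LVEF at six months".

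Section 7.3 first relates this variable to the primary outcome, with adjustment for the baseline factors listed in 7.1. It then goes further: "The interaction between improvement in left ventricular function and treatment assignment on even-free survival will then be assessed using a Cox proportional hazards model". The terms in that model are "improvement in left ventricular ejection fraction (treated as a binary effect), randomly assigned treatment, and their interaction, plus the aforementioned list of baseline risk factors". The display matches the model: "Kaplan-Meier plots will be presented stratified by improvement in left ventricular function and treatment assignment presented". A secondary version treats change in LVEF as linear.

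One safeguard is built in: "These analyses will be limited to patients who did not experience a primary outcome event in the first six months after randomisation". The section does not caution that the treatment contrasts within improvement strata are not protected by randomisation.

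The trial expects PCI to move LVEF. Protocol 2.2 gives the mechanism: "Improvement of blood flow by revascularisation of hibernating myocardium can lead to restoration of regional and global left ventricular function". Protocol 8.1 sizes the effect: "even half this sample size will provide 90% power to detect a minimum difference in EF of 4%, assuming a standard deviation of 11" percent.

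**The concern.** An interaction with a baseline variable compares arms that randomisation formed within each level of that variable. Section 7.1 does this properly, because viability is imaged before randomisation. Section 7.3 applies the same model form to a variable that treatment itself shifts.

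If PCI lifts some patients over the median who would otherwise have fallen below it, the PCI improvers are a different mix from the OMT improvers, and likewise for the non-improvers. Where LVEF change carries prognostic information beyond the measured baseline factors, the two arms within a stratum differ in prognosis before PCI has had any effect on events.

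What is at stake is interpretation. Four curves and an interaction p-value invite the reading that PCI helps, or harms, those whose ventricle recovers. The model cannot support that reading.

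**Working it through.** **The plan's own figure.** Section 7.3 states no number. The relevant one is the LVEF power statement in Protocol 8.1 (difference 4 points, SD 11, two-sided 5%, 90% power):

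n per arm = 2 × (1.960 + 1.282)² × 11² / 4² ≈ 159.

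Half of 700 is 175 per arm, which gives 92.5% power. The statement is reproduced, and a 4-point shift is a fair planning value for the effect of PCI on LVEF.

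**Assumptions not in the documents.** An unmeasured prognostic factor has a log hazard ratio of 0.7 (moderate) or 1.0 (strong) per SD. Its correlation with LVEF change is 0.5 (moderate) or 0.7 (strong). The SD of LVEF change is 11 (the Protocol gives 11 for EF, not for its change). Follow-up is 2 to 8.5 years. The true treatment hazard ratio is 1 for every patient unless stated.

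**Hand calculation, uniform gain of 4 points.** The pooled median change lies 2 points above the OMT mean and 2 below the PCI mean.

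- Share improved: Φ(2/11) = Φ(0.182) = 0.572 in PCI and 0.428 in OMT, so about 57% and 43%.
- Mean change the improvers would have had without PCI: 11 × 0.3924/0.572 = 7.5 in PCI; 11 × 0.3924/0.428 = 10.1 in OMT. The PCI improvers are worse by about 2.5 points.
- Among non-improvers the means are −10.1 in PCI and −7.5 in OMT, the same 2.5-point deficit.
- In SD units the deficit is 2.54/11 = 0.231. Moderate link: 0.5 × 0.231 × 0.7 = 0.081, and exp(0.081) = 1.08. Strong link: 0.7 × 0.231 × 1.0 = 0.162, and exp(0.162) = 1.18.

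So PCI looks mildly harmful in both strata, by about the same amount. The stratum hazard ratios are wrong while their ratio stays near 1.

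**Simulation of the 7.3 model.** Landmark at six months; Cox model on arm, improvement and their product; no covariate adjustment. Rejection rates come from 2,000 trials of 700; hazard ratios from 40 runs of 40,000.

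| Scenario | HR, not improved | HR, improved | Ratio | Interaction rejected |
|---|---|---|---|---|
| PCI does not change LVEF | 1.00 | 1.00 | 1.00 | 4.8% |
| +4 uniform, moderate link | 1.06 | 1.08 | 1.01 | 4.7% |
| +4 uniform, strong link | 1.13 | 1.16 | 1.03 | 6.7% |
| +4 on average, gain SD 6, strong link | 1.06 | 1.20 | 1.13 | 8.2% |
| +4 on average, gain SD 11, moderate link | 0.99 | 1.14 | 1.15 | 9.5% |
| +4 on average, gain SD 11, strong link | 0.96 | 1.27 | 1.32 | 20.9% |
| +4 on average, gain SD 11, factor unrelated to events | 1.00 | 1.00 | 1.00 | 4.5% |
| True HR 0.7, +4 uniform, moderate link | 0.80 | 0.79 | 0.98 | 5.9% |

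Without the improvement term, the arm comparison among landmark survivors gave 0.998 to 1.005 in every scenario with a true hazard ratio of 1. The distortion therefore comes from conditioning on improvement, not from the landmark. In the last row that comparison gave 0.75, so stratifying dilutes a real benefit.

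**Why the interaction moves only when the gain varies.** Gain unrelated to prognosis weakens the link between LVEF change and prognosis in the PCI arm alone. With gain SD 6 and a starting correlation of 0.7, it falls to 0.7 × 11/√(11² + 6²) = 0.61. With gain SD 11 it falls to 0.7 × 11/√(11² + 11²) = 0.49.

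**Milder inputs.** With a 3-point mean gain, gain SD 0, 4 or 6, log hazard ratio 0.7 and correlation 0.5, stratum hazard ratios are 1.01 to 1.08, ratios 1.01 to 1.07, and rejection about 5 to 6%.

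**Limit of the check.** The simulated trials had about 407 to 409 events in total in the null scenarios, against 300 planned. With fewer events the excess rejection would be smaller; the bias itself does not come from the number of events.

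**The case against.** Four points on the other side deserve weight.

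First, the safeguards are real. The landmark deals with early events and immortal time. The model adjusts for age, sex, previous heart failure admission, diabetes, ejection fraction, coronary extent, renal failure and test modality. If baseline covariates captured half of the prognostic variance, the stratum hazard ratios under the milder inputs would fall to about 1.00 to 1.06. This stands as a limit on size. It does not restore comparability, because adjustment reaches only measured factors.

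Second, a Cox interaction is symmetric. It also asks whether the prognostic value of improvement differs between arms, which is a legitimate descriptive question. In the varying-gain scenarios that difference is genuine. The term is false only as evidence that PCI works differently in patients who improve. This stands, and it shapes the fix.

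Third, a reader might infer that the interaction test is badly invalid, with large spurious effects to be expected. The documents do not support that. They give no variation of gain between patients and no strength of link to prognosis. A uniform gain leaves the test close to nominal, and the largest figures in the table need a strong link together with very uneven gains. Uneven gain is plausible, since section 3.1.1 asks whether viability predicts PCI's effect on recovery, but its size is unknown.

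Fourth, the stakes are limited. The analysis serves a secondary, exploratory objective of a sub-study. A reader might extend the objection to the trial's primary result or to 7.1. Neither conditions on a post-randomisation variable, so neither is touched.

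**Conclusion.** The point holds as one of interpretation and design. The treatment contrasts within improvement strata in 7.3 are not randomised comparisons, and the planned safeguards do not make them so.

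The bias needs two conditions: PCI changes LVEF, and an unmeasured factor drives both LVEF change and events. The first is the trial's premise, not a result in these documents. Without either condition the bias disappears.

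With an SD of LVEF change of 8 to 11 and a correlation with prognosis of 0.5 to 0.8, stratum hazard ratios are roughly 1.0 to 1.2 when the truth is 1. The interaction ratio is about 1.01 for a uniform gain and about 1.05 to 1.2 for a varying one. In the varying case the test rejects in about 5 to 15% of trials of 700. The stress case of 1.32 with 20.9% rejection lies beyond that range. The actual size cannot be known from the documents.

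**What to change.** In section 7.3 of the Viability Study SAP:

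- Keep the landmark analysis of LVEF improvement, binary and linear, against later events. Adjust it for randomised treatment and the 7.1 factors, and label it prognostic.
- Drop the treatment-by-improvement interaction test as evidence of effect modification, for both the binary and the linear version.
- Drop the PCI-versus-OMT comparisons within improvement strata. If four-group curves are shown, label them descriptive and non-randomised.
- Do not put a mediation analysis in their place as the cure. It needs the same untestable assumption, that no unmeasured factor drives both LVEF change and events.

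The cost is a change of wording and one model fewer. The plan loses stratum-specific treatment hazard ratios. Whether the effect of PCI depends on viability is still answered in 7.1 with a modifier measured before randomisation.
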